### 3.2 Subject disposition

The number and proportion of screened, randomized, treated and analyzed subjects will be provided. Where necessary, the CONSORT flow chart will be presented to describe the subject disposition in the statistical analysis report.

### 3.3 Primary and secondary data analyses

In primary and secondary data analyses, all stated hypotheses will be tested. In all analyses an error probability of  $\alpha = .05$  will be set a priori for descriptive statistics calculations. In addition to statistical significance, effect sizes (e.g., Cohen's  $d$ ) will be reported. Publication of results will follow CONSORT guidelines for transparent reporting of randomized trials.

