## 1. Study overview

To address the significant barriers to PrEP implementation for those who were assigned female at birth and self-identify as a woman and address racial inequities in HIV prevention in the United States (US), a novel approach that accounts for multilevel influences is necessary. This study is one part of a multi-component project and involves a patient-level intervention in one public health family planning clinic in Duval County Florida, where the majority of patients are women of color. The area has one of the highest HIV incidence rates among women in the US. The investigators developed a tablet-based decision support tool that helps users learn about HIV vulnerabilities and HIV prevention strategies to inform how they consider options for reducing their likelihood of acquiring HIV. Participants will be randomized to use the HIV decision support tool before their visit or standard counseling (without the use of the tool) and will be surveyed about the use of the tool, experiences with HIV prevention counseling, and intentions about the use of HIV prevention. A subset of participants, all individuals who self-identify as a woman and as Black or Latina, will also complete a post-clinic visit interview. The investigators will follow-up with participants at three months following their initial visit to see if they have initiated the HIV prevention method(s) they chose at their visit. The main outcomes will include a quantitative and qualitative assessment of PrEP or other HIV prevention use, decisional certainty, and satisfaction with information about HIV prevention options.

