### 1.1 Study objectives

Aim 1a: Women who use the HIV prevention decision support tool will be more likely to have initiated PrEP within 3 months compared to women who received standard counseling at the time of their initial appointment.

Aim 1b: The HIV prevention decision support tool will increase women's knowledge of PrEP and other HIV prevention methods compared to women who received standard counseling at the time of their initial appointment.

Aim 1c: The HIV prevention decision support tool will increase participants' decisional certainty in their choice of an HIV prevention method compared to women who received standard counseling at the time of their initial appointment.

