### 1.2 Study Design and Randomization

The study is a parallel-group Randomized Control Trial with up to 384 participants recruited from family planning sites in Duval County, Florida and randomized 1:1 into two groups (192 in intervention group, 192 in control). Study duration: 3 months.

Treatment: Participants in this arm will receive the HIV prevention DST intervention and will receive the intervention immediately before their provider visit.

Control: Participants in this arm will receive usual care.

Randomization procedures: Randomization will be implemented using randomly permuted blocks of randomly selected size 2 and 4, stratified by clinic and race. All randomization will occur by research staff with the use of a REDCap randomization instrument.

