### 1.5 Sample size calculation

Using standard methods, we estimate that a sample of 320 women will provide 80% power in two-sided tests with alpha of 0.05 to detect a between-group difference of 10 percentage points in PrEP uptake, from 5% among controls to 15% in the intervention arm. This estimate is conservative, for two reasons. First, in addition to multiple imputation, which will capture some information from women with missing 3-month outcomes, we will enroll 384 women to protect against a loss to follow-up of up to 20%. Second, because women rather than providers will be randomized, any within-provider clustering of outcomes will increase precision in the proposed mixed models including random effects for provider.

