## 2.2 Hypotheses

1. The intervention will result in significantly higher number of PrEP prescriptions compared to the control group.
2. The intervention will result in significantly higher number of individuals reporting PrEP initiation compared to the control group.
3. The intervention will result in significantly higher level of patient-perceived HIV risk post-visit compared to the control group.
4. The intervention group will report significantly higher PrEP knowledge compared to the control group.
5. The intervention group will report significantly higher quality of HIV care compared to the control group.
6. The intervention group will report significantly higher intention to initiate any HIV prevention method compared to the control group.
7. The intervention group will report significantly higher satisfaction with information received about HIV prevention compared to the control group.
8. The intervention group will report significantly higher confidence in decision to use an HIV prevention method compared to the control group.
9. The intervention group will report significantly higher acceptability of HIV prevention methods compared to the control group.
10. The intervention group will report significantly lower decisional conflict, as documented by the full scale and subscales, compared to the control group.
11. The intervention will result in significantly higher number of individuals reporting ongoing PrEP use at 3 months post-visit compared to the control group.
12. A significantly higher proportion of the intervention group will report use of any HIV prevention method at 3 months-post study initiation compared to the control group.
13. A significantly higher proportion of the intervention group will report significantly higher continuation of any HIV prevention method at 3 months-post study initiation compared to the control group.
14. The intervention group will report high acceptability of the DST.
15. A high proportion of the intervention group will report positive impression of the DST.
16. A high proportion of the intervention group will report willingness to use the DST at a future visit.
17. A high proportion of the intervention group will report willingness to recommend to a friend.
18. The intervention group will report high satisfaction with the DST.

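### Twelve between-arm secondary hypotheses and the decisional-conflict subscales are each tested at 0.05 with no ordering, correction or exploratory label, so secondary claims carry no overall error control

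*SAP*

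**What the plan says.** SAP 3.3 states that "In primary and secondary data analyses, all stated hypotheses will be tested". It fixes alpha at 0.05 for all analyses, with the unclear qualifier that this level "will be set a priori for descriptive statistics calculations".

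SAP 2.2 lists 18 hypotheses. H1 (PrEP prescriptions) is the primary. H2 to H13 compare the arms, and each predicts a significant difference. H10 is more than one test: "The intervention group will report significantly lower decisional conflict, as documented by the full scale and subscales, compared to the control group". H14 to H18 describe the intervention arm only, and SAP 3.3.2 plans summary statistics for them, so they are not counted here. SAP 3.3.2 assigns between-arm tests to H2-H9, H10 and H11-H13.

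Two other places bear on how much weight the secondary results will carry:

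- SAP 1.1 lists three aims side by side. Aim 1b concerns knowledge. Aim 1c reads "The HIV prevention decision support tool will increase participants' decisional certainty in their choice of an HIV prevention method", and no single test is assigned to it.
- SAP 1 says: "The main outcomes will include a quantitative and qualitative assessment of PrEP or other HIV prevention use, decisional certainty, and satisfaction with information".

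Neither document gives a hierarchy, a gate on H1, a multiplicity correction, or a statement that secondary results are exploratory.

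**The concern.** The 5% error rate applies to H1 alone. Each secondary hypothesis is written and tested as if it could be confirmed separately, so the chance that at least one reaches significance by luck grows with their number.

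This matters more than usual here, for three reasons. Two of the three stated aims rest wholly on secondary outcomes. Aim 1c could be claimed from the one-item confidence measure (H8), the full conflict scale (H10) or any subscale, and the SAP does not say which counts. H2-H13 are also all self-reported by participants who know their arm (Protocol 3.2.2, SAP 1.6).

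If H1 were null and one or two secondaries were significant, nothing in the SAP would tell a reader how much of that to expect by chance.

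**Working it through.** **Inputs from the documents**

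- Alpha 0.05 per test (SAP 3.3). Two-sidedness is stated only for the sample size (SAP 1.5), but the chi-square test named for most secondaries is non-directional, so two-sided testing is used throughout.
- Between-arm secondary hypotheses: H2-H9 (8) + H10 (1) + H11-H13 (3) = 12 (SAP 3.3.2).

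**Assumptions, because the documents give no figure**

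- Number of conflict subscales: 5. This gives 12 + 5 = 17 tests overall, and 1 (H8) + 1 (full scale) + 5 = 7 tests that could support Aim 1c.
- A common correlation rho between test statistics of 0, 0.3, 0.5 or 0.7.

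**The plan's own figure.** SAP 1.5 says "a sample of 320 women will provide 80% power in two-sided tests with alpha of 0.05", with uptake going "from 5% among controls to 15% in the intervention arm".

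- Per arm, n = [1.96 x sqrt(2 x 0.10 x 0.90) + 0.842 x sqrt(0.05 x 0.95 + 0.15 x 0.85)]^2 / 0.10^2 = 140.1, so 141.
- With continuity correction, n' = (n/4) x [1 + sqrt(1 + 4/(n x 0.10))]^2 = 159.5, so 160 per arm and 320 in total.

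The stated 320 is reproduced. It is sized for H1 only. The documents state no overall error rate for the secondary tests.

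**Independent tests, tool has no effect**

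- At least one significant difference in either direction: 1 - 0.95^m. For m = 12 this is 46.0%; for m = 17, 58.2%.
- At least one significant difference favouring the tool (2.5% per test): 1 - 0.975^m. For m = 12 this is 26.2%; for m = 17, 35.0%; for m = 7, 16.2%.

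**Correlated tests.** Take each statistic as Z_i = sqrt(rho) C + sqrt(1 - rho) e_i, with C and e_i independent standard normal. The chance of at least one favourable result is 1 minus the average over C of [Phi((1.96 - sqrt(rho) C)/sqrt(1 - rho))]^m. For either direction, Phi((-1.96 - sqrt(rho) C)/sqrt(1 - rho)) is subtracted inside the bracket. Simulation with 300,000 draws (12 and 17 tests) and numerical integration (all rows) agree to within about 0.2 percentage points.

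| Tests | Direction | rho 0 | 0.3 | 0.5 | 0.7 |
|---|---|---|---|---|---|
| 12 (H2-H13) | either | 46% | 40% | 32% | 23% |
| 12 (H2-H13) | favours tool | 26% | 20% | 16% | 12% |
| 17 (with 5 subscales) | either | 58% | 49% | 39% | 27% |
| 17 (with 5 subscales) | favours tool | 35% | 25% | 19% | 14% |
| 7 (Aim 1c) | favours tool | 16% | 14% | 11% | 9% |

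The comparator for the rows favouring the tool is 2.5%; for the rows in either direction it is 5%.

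**After the change.** With two named tests under Holm, the smaller p-value is compared with 0.05/2 = 0.025. If the tests are independent, the chance of any false positive among them is 1 - 0.975^2 = 4.9% in either direction, and 1 - 0.9875^2 = 2.5% in the tool's favour. A Bonferroni correction of all 12 would instead need 0.05/12 = 0.0042 per test.

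**The case against.** The strongest reply is that the primary claim is protected. Both documents name the same primary outcome, SAP 3.3.1 gives it one test, and no rule declares success from a secondary result. This stands, and it confines the point to secondary claims.

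Three further objections stand in part:

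- **The independent figures are on the high side.** H2 and H11 both concern self-reported PrEP use, and H12 and H13 both concern method use or continuation, so these results will overlap. Fisher's exact test is conservative for rare outcomes: with 5% in each arm and 160 per arm (an assumption), its true two-sided size is about 2.5%. In the other direction, the per-protocol repeat (SAP 2) and the data-driven collapsing and dichotomising of scales (SAP 3.1, 3.3.2) add chances not counted above.
- **The sentence on main outcomes in SAP 1 is a narrative summary.** The operative sections separate primary from secondary. A reader might infer that these domains will be reported as the trial's conclusions. The documents do not say so; the sentence only blurs the ranking.
- **The tie to descriptive statistics in SAP 3.3 might suggest that alpha carries no inferential weight.** That does not close the gap, because SAP 2.2 words the hypotheses as significant differences and SAP 3.3.2 assigns tests to them.

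A reader might also take the 46% as a one-in-two chance that a useless tool appears beneficial. The documents do not support this. The 46% includes differences against the tool. Reaching it for benefit alone would need independent one-sided tests at 0.05, which the SAP does not specify.

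**Conclusion.** The concern holds for secondary claims. H1 is unaffected.

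With no true effect and 12 tests, the chance of at least one false result favouring the tool is 26% if the tests are independent and 12-20% at correlations of 0.7 to 0.3. That is roughly five to ten times the 2.5% of a single test (11.6/2.5 = 4.6; 26.2/2.5 = 10.5). If five subscales are added it is 35%, or 14-25% when correlated. For Aim 1c alone it is 9-14% at those correlations.

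The count of 12, the 0.05 level and the absence of any control come straight from the SAP. The correlations and the five subscales are assumptions, and the percentages are approximate. The plan should be changed, but the gap does not undermine the trial's main test.

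**What to change.** In SAP 3.3, before analysis:

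1. Keep H1 as the only primary test, at 0.05.
2. Name one key secondary test for each remaining aim: for example H4 for Aim 1b and the H10 full-scale score for Aim 1c. Test the two by Holm at 0.05. The choice is the investigators' to make. H4 covers PrEP knowledge only, whereas Aim 1b also mentions other methods, and H8 is a direct one-item measure of certainty that could serve Aim 1c instead.
3. Report all other secondary outcomes and all subscales as between-arm differences with 95% confidence intervals, labelled exploratory and without significance claims.
4. Align the sentence on main outcomes in SAP 1 with this ranking, and reword the hypotheses in SAP 2.2 that become exploratory.

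Making the two key secondaries conditional on H1 is an option, not a requirement. SAP 1.1 lists the aims in parallel, and a gate would bar both whenever H1 fails. At the stated 80% power that is about 20% of the time (1 - 0.80), even if the planned effect on PrEP uptake is real.

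The cost is SAP wording only, with no extra participants or data. The downside is that some secondary results can no longer be called significant.

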#### 3.3.1 Primary analysis (H1)

PrEP prescriptions within 3 months of primary study visit will be extracted from participants' electronic medical records (EMRs). Data will be matched to survey data using participant medical record numbers (MRNs). Summary statistics will be presented by treatment group. Differences in PrEP prescriptions between groups will be examined by  $\chi^2$  or Fisher's exact-tests as appropriate. Effect size will be calculated.

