1.2 Study Aim

The aim of this study is to determine the effects of an HIV prevention DST coupled with standard counseling on women's PrEP initiation at reproductive health clinics in Duval County, Florida.

Approximately 384 women presenting to two reproductive health clinics in Duval County, Florida, will be randomized to standard counseling plus use of an HIV prevention DST, providing education about PrEP and encouraging self-assessment of HIV risk, or standard counseling alone. The primary outcome of interest is PrEP initiation, with additional quantitative and qualitative evaluation of women's experiences of care and quality of decision making.

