 - Researchers will also ask patients if they self-identify as Black or Latina, or multiracial including Black or Latina, to determine eligibility for randomization to interviews or audio-recordings after randomization to the study.
- If participants are eligible, they will be consented to enroll in the study.
 - If individuals decline to enroll or are ineligible, the reason for ineligibility will be recorded or reason for declining if shared.
- All participants will be asked to complete a contact information form in REDCap on a tablet computer and complete a pre-visit survey collecting information on experience with and knowledge of HIV prevention.
- Participants will then be randomized to the intervention arm (DST) or control (standard care).
- Based on response during eligibility screening regarding racial identity, participants will then be randomized to determine if they will be invited to conduct a qualitative interview or audio-recording of their counseling visit. Specifically:
 - Participants who identify as Black or Latina will be randomized to participate in a qualitative interview or audio-recording
 - Participants who do not identify as Black or Latina will be randomized only to audio-recording or not.
- Participants who are randomized to participate in an interview will be invited to have an interview the same day if the qualitative interviewer is available. Interviews will

be conducted either in-person in a private space, or over Microsoft Teams or Zoom (using a hotspot), both HIPAA compliant video conferencing programs. Interviews will be conducted within 1 week of the clinic visit.

- Participation in each study activity (participation to be randomized to the DST or standard care, participation in a qualitative interview, and/or participation in an audio-recorded clinic visit) will require a unique consent. Participants randomized to the audio recordings will be consented for the audio recording at this time. Participants who are randomized to participate in an in-depth interview and interested in being interviewed, will be consented by [name], a member of the study team, or another study staff member, on the day of the interview before the interview begins.
 - If participants decline to enroll in additional study components, their reason for declining will be recorded and they will be allowed to continue with primary study activities.

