10.1 Methods of Quantitative Data Analysis

See Statistical Analysis Plan.

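### The primary test ignores the clinic and race randomisation strata, and the provider mixed model credited in the sample-size text is specified nowhere

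*SAP*

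**What the plan says.** - **Randomisation.** SAP 1.2 uses permuted blocks of 2 and 4, 1:1, "stratified by clinic and race".
- **Primary test.** SAP 3.3.1 states "Differences in PrEP prescriptions between groups will be examined by" a chi-square or Fisher's exact test. It names no stratum, covariate or provider term. It promises an effect size without naming the measure or an interval. SAP 3.3 offers Cohen's d as an example.
- **Sample size.** SAP 1.5 and Protocol 7.2 claim "80% power in two-sided tests with alpha of 0.05" with 320 women, for 5% versus 15%. They call this conservative on two grounds, the second being that "any within-provider clustering of outcomes will increase precision in the proposed mixed models including random effects for provider".
- **Where the model should be.** Protocol 10.1 reads only "See Statistical Analysis Plan". SAP 3.1 and 3.3.2 list t-tests, sign tests, chi-square and Fisher tests.
- **The strata.** SAP section 1 refers to "one public health family planning clinic". Protocol 1.2 has "Approximately 384 women presenting to two reproductive health clinics". SAP 1.2 gives no race categories. The only race item described is in Protocol 3.2.3 ("Researchers will also ask patients if they self-identify as Black or Latina, or multiracial including Black or Latina"), where it serves selection for interviews and audio-recordings.

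**The concern.** Stratified randomisation makes the arms more alike within clinic and race. If PrEP uptake differs between strata, an analysis that ignores them overstates the variance of the treatment difference. The test becomes slightly conservative, and precision already bought at randomisation is not collected.

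The second problem is one of consistency. The sample-size text takes credit for a provider mixed model, while the analysis section plans a two-by-two table. The claimed margin belongs to an analysis that is not planned, and the two texts leave open which analysis is primary. That should be settled before anyone sees outcomes by arm. The same edit can repair a related gap: for a binary primary outcome, neither the effect measure nor its confidence interval is fixed in advance.

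**Working it through.** **1. Reproduce the plan's 320.** Inputs from SAP 1.5: p₁ = 0.05, p₂ = 0.15, difference d = 0.10, two-sided alpha 0.05 (z = 1.960), power 80% (z = 0.842), 1:1 allocation. The mean rate is p̄ = 0.10.

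Without continuity correction, per arm:

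n = [1.960·√(2·0.10·0.90) + 0.842·√(0.05·0.95 + 0.15·0.85)]² / 0.10² = (0.8315 + 0.3521)² / 0.01 = 140.1, so 141 per arm and 282 in total.

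With continuity correction:

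n′ = (n/4)·[1 + √(1 + 4/(n·d))]² = 35.02·[1 + √(1 + 4/14.01)]² = 159.5, so 160 per arm and **320 in total**.

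The figure matches exactly and contains no stratum or provider term. The mixed model contributed nothing to it.

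**2. Power of the planned tests (exact enumeration, 5% vs 15%).**

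| Per arm | Chi-square | Fisher |
|---|---|---|
| 160 | 86.8% | 82.4% |
| 192 | 92.1% | 89.1% |

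Both exceed 80% at 320 without any adjustment.

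**3. What stratifying adds.** The documents give no stratum-specific rates, so the rates below are assumptions, all averaging 5% in controls. The simulation used 384 women, blocks of 2 and 4 within strata, and a common odds ratio set to give 15% overall in the treated arm. There were 20,000 replicates per scenario (simulation error about 0.2 points for power and 0.15 for type I error).

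| Strata | Control rates (%) | Power unadjusted | Power CMH |
|---|---|---|---|
| Four equal | 5/5/5/5 | 91.9 | 91.8 |
| Four equal | 2/4/6/8 | 92.4 | 92.5 |
| Four equal | 1/1/9/9 | 93.1 | 93.8 |
| Four equal | about 0/1/7/12 | 93.0 | 94.1 |
| Two clinics, race 75/25 | 6/6/2/2 | 92.1 | 92.3 |
| Two clinics, race 75/25 | 3.5/8.5/1/3 | 92.6 | 92.8 |
| Race only, 288/96 | 6/2 | 92.1 | 92.3 |
| Race only, 192/192 | 8/2 | 92.7 | 93.1 |
| Race only, 288/96 | 3/11 | 92.4 | 92.9 |

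Differences run from −0.1 to +1.1 points. Type I error was 4.1 to 4.9% unadjusted and 4.3 to 5.2% for CMH. The mean 95% CI half-width for the risk difference was 5.9 points unadjusted and 5.5 to 5.9 stratified.

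A separate simulation at 320 women (four equal strata, 100,000 runs) agrees:

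| Odds ratio per factor | Power unadjusted | Power CMH | Type I error unadjusted |
|---|---|---|---|
| 1 | 86.8% | 86.7% | 4.9% |
| 2 | 87.0% | 87.2% | 4.7% |
| 3 | 87.4% | 88.2% | 4.5% |
| 5 | 88.1% | 89.7% | 4.2% |

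CMH type I error was about 4.9% throughout.

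**4. What provider adjustment might add.** The documents give no intraclass correlation (ICC). Assuming 320 women and 10 equal providers, with a CMH test by provider standing in for the mixed model (40,000 runs):

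| ICC | Unadjusted | Provider-adjusted |
|---|---|---|
| about 0 | 86.6% | 85.4% |
| 0.02 | 85.1% | 85.1% |
| 0.05 | 82.5% | 83.9% |
| 0.10 | 79.7% | 83.3% |

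Rows should not be compared with one another, because the simulated treated rate drifts from 15.0% to 14.3% down the table. Within rows, adjustment helps only at the two higher ICCs, so a gain from any degree of clustering is not assured.

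**The case against.** The strongest reply is that the planned test is valid, already exceeds 80% power at 320, and need not be replaced. The larger gains come only from strong assumed contrasts between strata; with no stratum effect the difference is within simulation noise. All of that stands and limits how much weight the point can carry. It does not argue for leaving the strata out: CMH did no material harm in any scenario, and its type I error stayed at or below 5% in a check at 1% uptake.

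A second reply is that deleting the clustering sentence leaves the claim of conservatism resting on its other ground, which is also weak. SAP 4.2 imputes baseline characteristics only, and 384 is 320 × 1.2, whereas 20% loss requires 320/0.80 = 400 (384 × 0.80 ≈ 307). This is correct, but it is a separate defect that the deletion neither creates nor worsens. The paragraph is best revised as a whole.

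Third, SAP 3.3 does mention Cohen's d. It does so only as an example; it is not a natural summary of 5% versus 15%, and no interval is stated.

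Fourth, the one-clinic statement is the outlier, since SAP 1.2 itself speaks of sites in the plural. That is fair, and it makes the point a minor reconciliation. Finally, a provider identifier could be held in survey or REDCap fields not shown; its absence from the chart-extraction list does not prove it is unrecorded.

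**Conclusion.** The concern holds on both counts. The primary test omits the randomisation strata, and the provider mixed model is invoked for precision but never specified. The consequence is small: about 0 to 1 point of power at 384 women and up to 1.6 points at 320, with no type I error inflation and no effect on the stated 80% power. These sizes rest on assumed stratum rates, stratum sizes and a common odds ratio; the textual findings do not. The change should be made because it costs almost nothing, fixes the primary estimate in advance, and removes a margin that the planned analysis will not deliver. It is not a correction of an invalid design.

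**What to change.** 1. Reconcile the number of clinics between SAP section 1 and Protocol 1.2. State the race categories used in the allocation table, including whether they are the Black/Latina screening item.
2. In SAP 3.3.1, write:

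> The primary test of H1 is a two-sided Cochran-Mantel-Haenszel test at alpha 0.05, stratified by the randomisation factors (clinic and race). The primary estimate is the Mantel-Haenszel stratum-weighted risk difference in PrEP prescription within 3 months, with 95% CI. The unadjusted chi-square or Fisher test is supportive.

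   If only one clinic takes part, stratify by race alone.
3. Delete the within-provider clustering sentence from SAP 1.5 and Protocol 7.2, and adjust the count of reasons to match. The alternative is to specify the model fully: link, fixed effects, estimand and fallback.

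**Cost.** Steps 1 to 3 need SAP and protocol wording and a few lines of Stata. Clinic and race are required at randomisation, so no new data are needed. Keeping the provider model is not free. The chart-extraction list in Protocol 3.2.5 has no provider identifier, so its capture would have to be confirmed. A logistic provider model was also not tested here with so few expected control events (192 × 0.05 ≈ 10).
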